3.2.4 SAFETY

OBJECTIVES	ENDPOINTS	JUSTIFICATION FOR ENDPOINTS
Safety		

 • To compare, between the same two groups, 
 1) The rate of solicited adverse events (AEs) through 3 days after each injection (dose 1, 2 and 3) 2) The rate of unsolicited adverse events and serious adverse events (SAEs) through four weeks after first injection • As a secondary objective, sub-group analysis for potential effect measure modification of safety endpoints by sex (males or females) 	
 1. Number of solicited self-reported events over three days following each injection of the following adverse events: 
 a. Local reactions (limited to the site of the injection): pain, erythema, oedema, pruritus and induration. b. Systemic reactions: fever, shivering, malaise, asthenia, faintness, dizziness, headache, myalgia, arthralgia, nausea and abdominal pain. c. Hypersensitivity or allergic reactions: anaphylaxis, urticaria, rash and erythema multiforme. 2. Number of unsolicited adverse events and SAEs reported to RUSVM Student Health Services through four weeks after first injection 	
Solicited adverse events are those adverse events listed in the package insert of the study intervention (Rabivax-S rabies vaccine)

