12 DATA COLLECTION METHODS

After enrollment, participants will complete a questionnaire that will capture data on relevant baseline characteristics including sex, age, health and vaccination status. (Baseline CRF; Appendix C). Participants will complete a short survey each week, starting in study week 3, to capture self-reported episodes of illness (respiratory, diarrheal and febrile illness; Primary Endpoint and Secondary Endpoints 1-5) in the preceding week (Appendix G). Surveys will be sent by email to all participants each Monday. Participants who have not completed the survey by Wednesday afternoon will be sent a request by email to complete the survey for the preceding week. Surveys will be sent weekly, for 26 weeks. A participant is considered to have completed the study one week after receipt of the final (26th) weekly survey for that participant's cohort.

As an incentive to enhance participant retention and response rates in weekly illness surveys, all participants who complete a weekly survey will be entered into a draw each week for a chance to win a EC\$25 gift voucher to a food/beverage vendor on the RUSVM campus. Selection of a winner each week will be done by computer-generated random sampling. The weekly winner will be notified by email in the week following the draw.

Clinically- and laboratory-confirmed episodes of study syndromes (Secondary Endpoints 6 & 7) will be collected by study personnel at RUSVM Student Health Services, as part of the

routine clinic visits and diagnostics. At the end of each 26-week observation period for each study cohort, data from that cohort will be compiled by the director of the RUSVM Student Health Services, anonymized to protect privacy and aggregated by study arm, before being sent to the Data Analyst who will conduct the analysis.

Occurrence of expected Adverse Events (Safety Endpoint 1) will be solicited in an online survey (Appendix H) sent to participants 3 days after receiving an injection (for dose 1, 2 and 3). Occurrence of unsolicited adverse events and serious adverse events (Safety Endpoint 2) will be captured by study personnel at RUSVM Student Health Services through completion of an Adverse Event form (Appendix I; See **Section 15.3, Identification of Adverse Events** for details).

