15.3 IDENTIFICATION OF ADVERSE EVENTS

The Study Coordinator will review the Visit 1-3 CRFs daily for participants receiving injections (dose 1, 2 or 3). The study coordinator will send a link to an online Qualtrics survey (Appendix H) by email on day 3 after the date of the injection (dose 1, 2 or 3) to all participants. Information on occurrence of expected AEs will be specifically solicited in the survey, by asking the question, “Since receiving the study injection 3 days ago, did you experience any of the following...?” and providing participants with a list of expected AEs (see **Section 15.2, Classification of adverse events** for details) from which to select. Participants will also be asked to grade the severity of any AEs (mild, moderate or severe) and the outcome (recovered/resolved without sequelae, recovered/resolved with sequelae or ongoing). Information on occurrence of other AEs (unsolicited) will be sought by asking the question, “Besides the signs listed above, have you noticed anything different since starting the study?”, and providing participants the opportunity to describe what they noticed or experienced, and grade the severity and outcome as above.

Participants will also be encouraged to report any adverse events to RUSVM Student Health Services (unsolicited adverse events). An adverse event form (Appendix I) will be completed for all adverse events reported to RUSVM Student Health Services, using the Vaccine Adverse Event Reporting System (VAERS) writable PDF form (https://vaers.hhs.gov/pdf/vaers_form.pdf). The Principal Investigator, together with the

Director of the RUSVM Student Health Services, will review and compare the reports of unsolicited adverse events (adverse event forms) against reports of solicited adverse events in the AE surveys, to avoid double capture.

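### Safety Endpoint 2 is worded to count only events reported to Student Health Services, although the post-dose survey also collects unsolicited adverse events inside the same four-week window

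*Combined protocol and SAP*

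**What the plan says.** Section 3.2.4 sets the second safety objective as a between-arm comparison of "The rate of unsolicited adverse events and serious adverse events (SAEs) through four weeks after first injection". It names no reporting route. The endpoint beside it is narrower: "Number of unsolicited adverse events and SAEs reported to RUSVM Student Health Services through four weeks after first injection". Section 12 repeats the narrower version: "Occurrence of unsolicited adverse events and serious adverse events (Safety Endpoint 2) will be captured by study personnel at RUSVM Student Health Services". It says this is done on the Adverse Event form (Appendix I) and refers the reader to Section 15.3 for details.

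Section 15.3 describes two streams.

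- **Survey.** The study coordinator emails an online survey three days after each dose. Besides the list of expected events, it has an open part: "Information on occurrence of other AEs (unsolicited) will be sought by asking the question" whether participants "have you noticed anything different since starting the study". Participants describe the event and grade its severity and outcome.
- **Clinic.** Participants are encouraged to report events to Student Health Services, and "An adverse event form (Appendix I) will be completed for all adverse events reported to RUSVM Student Health Services".

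To prevent counting an event twice, the investigator and the clinic director are to "compare the reports of unsolicited adverse events (adverse event forms) against reports of solicited adverse events in the AE surveys".

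**The concern.** Safety Endpoint 1 is limited to a fixed list of solicited reactions. An event that a participant volunteers in the survey's open question, and does not also report to the clinic, is not on that list and did not come through the clinic. As worded, it belongs to neither safety endpoint, although the trial asked for it and stored it.

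The two routes also differ in quality for a comparison between arms. The survey puts the same question, at the same interval after each dose, to every participant, and participants are blinded (Section 11.3). The clinic route depends on who chooses to report, and the form is completed by staff at the site where study personnel open the allocation envelopes and look up allocation before doses 2 and 3 (Section 11.2). A literal reading keeps the less uniform source and discards the more uniform one. Because another reading is possible, two analysts working from the same data could also report different totals for Safety Endpoint 2.

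**Working it through.** The plan gives no figure for this endpoint to reproduce. The check is one of dates and of wording.

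**1. Does the window explain the exclusion?** Inputs: doses on days 0, 7 and 21 (Section 6.3); survey 3 days after each dose (Section 15.3); window of 4 × 7 = 28 days from first injection (Section 3.2.4).

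- Dose 1 survey: 0 + 3 = day 3
- Dose 2 survey: 7 + 3 = day 10
- Dose 3 survey: 21 + 3 = day 24

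All three are at or before day 28, so timing does not exclude them. A survey goes out after the window only if its dose is given later than day 28 − 3 = 25. On schedule the last survey precedes the end of the window by 28 − 24 = 4 days. Events starting after that survey rest on clinic reports alone, in both arms alike.

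**2. Where does each kind of report go?**

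- Listed reaction ticked in the survey: Safety Endpoint 1.
- Unlisted event reported to the clinic by day 28: Safety Endpoint 2.
- Unlisted event written in the survey by day 28 and not reported to the clinic: within Objective 2, but in neither endpoint as worded.

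**3. Does any section carry the survey answers across?**

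- Section 12 sends the reader to Section 15.3 for Safety Endpoint 2, and Section 15.3 contains the open question. That points towards inclusion. The same sentence, however, names clinic personnel and the Adverse Event form as the means of capture.
- Section 15.2 has the clinic manager assess the relationship to study intervention for all adverse events. That governs causality assessment. It does not say what the endpoint counts.
- Section 15.3 has a form completed for events reported to the clinic. It does not say that survey answers are transferred to forms.
- The double-capture check sets clinic forms against solicited survey reports only. Had open answers been meant to count, they would need the same check, and none is stated.

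**4. What if both sources are simply pooled?** Each survey's open question looks back to the start of the study. An event starting on day 1 could be written in the surveys of days 3, 10 and 24 and also reported to the clinic: 3 + 1 = 4 records of one event. Pooling therefore needs a de-duplication rule, and the plan has none for open answers.

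**5. What else depends on this?** Section 8 sizes the trial on illness-episode rates, and Section 14 tests those rates. Safety Endpoint 2 enters neither.

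**The case against.** The strongest reply is that the plan, read as a whole, already includes the survey answers. Objective 2 is unrestricted, Section 12 points to Section 15.3, and Section 15.2 speaks of all adverse events. This stands as a reasonable reading, and it is why the survey events cannot be called definitely lost. It does not settle the matter, because the endpoint and the capture sentence both name the clinic and no step links the survey to the form. Section 14 promises fuller methods for the primary and secondary endpoints and does not mention the safety endpoints.

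A reader might also infer a larger defect: that serious events after day 28 are wrongly left out of the between-arm comparison, since Section 15.4 sends all serious events to the IRB with no stated time limit. The documents do not support calling this an error.

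- The objective and the endpoint both give four weeks, and the schedule of activities marks unsolicited events only in the early weeks. The window is a consistent, prespecified choice.
- No section describes asking about serious events after the dose surveys, so later ones become known only if someone reports them. A rate or upper limit calculated to exit would assume complete ascertainment that the plan does not describe.
- A hospital admission for respiratory, diarrheal or febrile illness would meet the serious-event definition in Section 15.1 and could also be an efficacy outcome. Clinic study staff would know the participant's allocation.

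**Conclusion.** The point holds as a minor mismatch between Objective 2 and the wording of Safety Endpoint 2 and its capture route. All 3 of the 3 on-schedule surveys fall within the 28-day window, so a literal analysis would set aside unsolicited events already collected from blinded participants. Whether that would happen depends on which reading the analyst takes.

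The number of events affected cannot be derived, because the documents give no expected rate of volunteered events and no estimate of how many would also reach the clinic. The survey dates assume doses given on schedule. Appendices H and I are not in the supplied text, so it is not known whether the survey asks for an onset date. Serious events still go to the IRB once the investigator is aware of them, so oversight is unaffected, as are the primary endpoint, sample size and Type I error.

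**What to change.** Define Safety Endpoint 2 as unsolicited adverse events and serious adverse events with onset within four weeks of first injection, from either the Adverse Event form or the survey's open question. State a de-duplication rule that works across the two sources and across one participant's repeated surveys, using onset date. Reconcile Sections 3.2.4, 12 and 15.3 accordingly, and extend the double-capture check to open answers. Reporting the count by source beside the total would show how much each route contributes.

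The cost is a wording amendment, some matching work, and an onset-date item if the survey lacks one.

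Optionally, and not to correct an error, list by arm any serious events that become known to the study between day 28 and exit. Describe them as passively ascertained and possibly overlapping the efficacy outcomes, and attach no rate limits or between-arm inference. The four-week window can stay as it is.

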6.3 DOSING AND ADMINISTRATION

Dosing and administration of the vaccine (Rabivax-S) will be according to the package insert, following the schedule for pre-exposure prophylaxis via the intramuscular route; that is, 1 mL by intramuscular injection in the deltoid area of the arm on Day 0, Day 7 and Day 21. Dosage and administration of the placebo (sterile water for injection) will follow the same schedule and route of administration; that is, 1 mL by intramuscular injection in the deltoid area of the arm on Day 0, Day 7 and Day 21. In the event of interruption of the schedule of administration (of either the vaccine or the placebo), the schedule will be

resumed without repeating a previous dose (as per Table 3 Recommendations for Interrupted or Delayed Routine Immunization – Summary of WHO Position Papers, updated April 2018; http://www.who.int/immunization/policy/immunization_tables/en/).

Vaccine and placebo will be administered to participants at the RUSVM Student Health Services by study nurses or nurse practitioner, using a 25G (0.50 x 25mm) needle and 2 mL syringe.

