6.5 DISCONTINUATION OF STUDY INTERVENTION

Prior to administration of each dose of either the vaccine or placebo, participants will be assessed by personnel at the RUSVM Student Health Services for contraindications to the vaccine (see **Section 5.2.3, Screen Failures** for listed contraindications). Individuals with a contraindication requiring postponement of vaccination may return once the condition is resolved to resume the intervention for their allocated group (vaccine or placebo), so long as this occurs before study completion (see **Section 7, Participant Timeline** for definition of study completion). In the event of interruption of the schedule of administration (of

either the intervention or the control), the schedule will be resumed without repeating a previous dose (see **Section 6.3, Dosing and Administration** for details).

Participants for whom the study intervention was halted, due to absolute contraindications or other clinically-relevant event, or for whom intervention was postponed beyond the time of study completion, will remain in the study and complete the weekly illness surveys.

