7 PARTICIPANT TIMELINE

Students will be informed about the trial prior to the start of the semester for which they are eligible (orientation week for VP and 1st semester cohorts, and at the end of 4th semester for 5th semester cohorts). Students will be recruited into the study during orientation week and/or the first week of the semester, and will receive the first injection (day 0) within the first two weeks of the semester. Participants will receive the second injection on day 7 and the third injection on day 21. If necessary, participants can begin the intervention later, so long as day 0 falls within the first 12 weeks of the semester (see **Section 5.2.2, Exclusion criteria** for details).

Weekly illness surveys will begin in study week 3 (Monday of study week 3, day 10-14 after first injection) for all participants, and will continue for 26 weeks (through week 11 of the following semester in the case of a two-week semester break, or week 10 of the following semester in the case of a three-week semester break). One week after receipt of the final (26th) weekly survey, participants will be unmasked and will exit the study. Following exit, participants who were allocated to the control group will begin a primary course of rabies

vaccine in weeks 11 or 12 (depending on 3- or 2-week semester break), to be completed by the end of the semester (weeks 14 or 15).

A participant is considered to have completed the study one week after receipt of the final (26th) weekly survey.

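### The between-arm comparison of unsolicited AEs and SAEs stops at day 28, so it covers 7 days after an on-schedule third dose and none after a dose given from day 29

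*Combined protocol and SAP*

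**What the plan says.** Section 3.2.4 sets two safety endpoints with different anchors. Endpoint 1 is tied to every dose: "Number of solicited self-reported events over three days following each injection". Endpoint 2 is tied to the first dose only: "Number of unsolicited adverse events and SAEs reported to RUSVM Student Health Services through four weeks after first injection". The matching objective 2 has the same limit.

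Section 6.3 schedules doses on days 0, 7 and 21 and has an interrupted course picked up again with no dose repeated. Under section 6.5, a participant whose dose was postponed for a temporary contraindication may "resume the intervention for their allocated group (vaccine or placebo), so long as this occurs before study completion". Section 5.2.3 lists fever or acute illness among the reasons for postponement.

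The first-dose anchor also appears elsewhere. Section 15.4 times the safety report to the manufacturer for the first two cohorts by four weeks of follow-up from dose 1. The unsolicited-AE row of the schedule of activities (section 7.1) carries four marks.

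On data capture, section 12 takes endpoint 2 from AE forms completed at Student Health Services. Section 15.3 has a form completed for every AE reported there and states no cut-off date. Section 6.4 records the date of each dose.

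**The concern.** The third dose completes the course, and it has the shortest follow-up in the one comparison the documents plan for unsolicited AEs and SAEs as such. A delayed dose may have none. For example, an SAE on day 35, two weeks after an on-schedule third dose, would go to the IRB under section 15.4 and could be on an AE form, yet it would not enter the comparison of arms. What is at stake is how complete the randomised safety comparison is. The efficacy results, sample size and alpha are not affected.

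**Working it through.** The plan states no coverage figure to reproduce, so the check is day arithmetic.

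**Inputs.** The window ends on day 28 (section 3.2.4). Doses fall on days 0, 7 and 21 (section 6.3). Late doses are allowed (sections 6.3 and 6.5).

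**Days counted after a dose** = max(0, 28 − day of dose).

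| Dose | Day given | Days counted |
|---|---|---|
| 1 | 0 | 28 |
| 2 | 7 | 21 |
| 3, on schedule | 21 | 7 |
| 3, late | 25 | 3 |
| 3, late | 28 | 0 (same-day events at most) |
| 3, late | 29 or later | 0 |

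Dose 3 falls wholly outside the window once it is 29 − 21 = 8 days late.

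**How late a postponed dose can be.** The limit is study completion. Section 7 says "Weekly illness surveys will begin in study week 3 (Monday of study week 3, day 10-14 after first injection) for all participants". Survey 26 comes 25 weeks after survey 1, and completion is one week after that: 10 + 175 + 7 = day 192, to 14 + 175 + 7 = day 196. Section 12 instead refers to "one week after receipt of the final (26th) weekly survey for that participant's cohort". If surveys run by cohort, a participant starting in week 12 rather than week 2 completes 70 days earlier, at day 122 to 126. Both are well past day 28, so the point does not depend on which reading is meant.

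**Coverage as a share.** This needs a reference length of follow-up per dose, which the documents do not give, so the figures below are assumptions shown as a range.

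| Assumed reference after each dose | Dose 3, on schedule | All three doses |
|---|---|---|
| 7 days | 7/7 = 100% | (7 + 7 + 7)/21 = 100% |
| 14 days | 7/14 = 50% | (14 + 14 + 7)/42 = 83% |
| 28 days | 7/28 = 25% | (28 + 21 + 7)/84 = 67% |

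The 28-day row applies the plan's own four weeks after dose 1 to every dose. In calendar days, four weeks after an on-schedule dose 3 is day 21 + 28 = 49, and the current window covers 28/49 = 57% of that span.

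**What continues after day 28.**

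- Solicited AEs are compared for 3 days after every dose, late or not (section 3.2.4).
- All SAEs, and related unexpected nonserious AEs, go to the IRB (section 15.4). These are not described as a comparison of arms.
- The manufacturer receives safety data, for later cohorts within 30 days of cohort exit (section 15.4). This is not described as a comparison of arms either.
- Respiratory, diarrheal and febrile illness is compared by arm over 26 weeks, and so are clinic visits for four such diagnosis codes (sections 3.2.1, 3.2.2 and 14).

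None of these compares other unsolicited AEs, or SAEs as such, by arm after day 28.

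**Effect of a fixed day-49 window.** It gives 49, 42 and 28 days after on-schedule doses. A dose 3 on day 28, 35 or 42 gets 21, 14 or 7 days.

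**The case against.** The strongest defence is that day 28 is a deliberate and consistent choice. The objective, the endpoint, the first-two-cohort report and the schedule row share the same anchor, and measured against its own window the plan's coverage is complete. This stands: the point is an improvement in coverage, and the percentages depend on the reference chosen.

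A second argument is that by-arm follow-up does not really end on day 28. The AE definition in section 15.1 takes in any symptom or disease, so the 26-week illness comparison is itself a comparison of one class of AE. This also stands, and it narrows the gap to events other than the study illnesses, and to SAEs counted as SAEs.

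A third argument is that late doses may be rare. The third dose must slip by at least 8 days to lose all coverage, and no frequency is given. That limits the weight of the late-dose part. The 7 days after an on-schedule dose 3 apply to everyone who follows the schedule.

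Finally, a day-49 window does not reach every late dose, and simply listing later AE forms by arm would be lighter. The first half is true, which is why the fix adds a supportive list. A listing alone would leave the endpoint itself ending on day 28.

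**Conclusion.** The point holds as a modest limit on the safety comparison. Endpoint 2 counts 28, 21 and 7 days after on-schedule doses 1, 2 and 3, and nothing after a dose from day 29. These figures follow directly from the text. The number of missed events cannot be computed, because the documents give neither an event rate nor a frequency of late doses.

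A reader might infer more, but the documents do not support it:

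- **A contradiction with section 6.5.** Allowing a late dose and fixing a day-28 count are compatible.
- **Bias between arms.** The window is the same in both arms.
- **Unmonitored late events.** The day-3 surveys, IRB reporting and manufacturer reporting continue.
- **A breach of a required four weeks per dose.** No such requirement is stated.

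Whether answers to the open question in the day-3 survey (section 15.3) count in endpoint 2 is a separate matter of wording and not part of this point.

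**What to change.** 1. Extend the objective 2 and endpoint 2 window to a fixed day 49 from first injection in both arms. Keep the day-28 count for the first-two-cohort manufacturer report in section 15.4.
2. As a supportive table, list by arm the unsolicited AEs and SAEs that occur within four weeks after any injection actually received, counting an event once where windows overlap. Stop at study exit or unmasking, because section 7 states "Following exit, participants who were allocated to the control group will begin a primary course of rabies" vaccine, and section 9 extends this to controls who withdraw. The table depends on doses received after randomisation, so it should not replace the fixed-window comparison.
3. Align the unsolicited-AE row of the schedule of activities with the new window.

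Dosing is unchanged. The cost is a few more AE forms and one more table, since forms have no stated cut-off and injection dates are already recorded.

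Day 49 precedes study completion on either reading of the survey calendar. For a first dose in week 2 it falls in semester week 9. Section 7 also says "participants can begin the intervention later, so long as day 0 falls within the first 12 weeks of the semester". For a first dose in week 12, day 21 falls in week 15, day 28 in the first week of the break, and day 49 in week 2 or week 1 of the next semester after a two- or three-week break. If some students are away then, reporting may be weaker, and a reminder to report events from the break would help.
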